3. INVESTIGATIONAL PLAN

3.1. Study Design

Fifteen patients (approximately 80% children) with WAS/ XLT will be enrolled and undergo baseline screening including not only blood drawing but also history of illness in the past, while ten additional WAS and XLT otherwise ineligible or unwilling patients who will not undergo study treatment and ten control subjects will undergo a one-time blood draw. The pediatric control and non-treatment WAS/XLT subjects will be pediatric patients who are having their blood drawn for reasons not related to an acute illness and will provide a limited amount of additional blood. The pediatric control and non-treatment WAS/XLT subjects will have their blood drawn at Cornell after giving consent. They will not be asked for more than 5-10 ml of blood per year of age up to a maximum of 30 ml total in one draw. Blood drawn will be studied for stem cells and

megakaryocytopoiesis, Immature Platelet Fraction (IPF), and platelet function (see table). These subjects will have their blood drawn for another purpose e.g. pre-op clearance for surgery and therefore it will be a small amount of extra blood posing a minimal risk to the subject. Subsequently, treatment patients will start on 2 mg/kg of eltrombopag and be seen every two weeks in the first month, and monthly for the first year. Although Promacta is commercially available in 25 mg and 50 mg tablets, it is also available for clinical studies in 12.5 mg tablets which will be provided by Novartis for this study. In this study, the starting dose will be based upon weight; patients over 50 kg will start at 50 mg daily unless they are of East Asian origin in which case they will use 25 mg as their initial dose. The dose of eltrombopag will be titrated for each subject based on their platelet response (see table 1). Overall, in this study, doses between 12.5mg every other day and 75mg once daily are anticipated to be required to maintain platelet counts between 50 and 400Gi/L. However, as explained in the provided dosing guidelines, the dose of eltrombopag will be reduced whenever the platelet count exceeds 200Gi/L in order to prevent it from reaching 400Gi/L. The goal is to have a platelet count in a safe hemostatic range, albeit not necessarily a normal platelet count.

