- (4) ALT levels are ≥ 5 times ULN.
- If a subject has an adverse experience that would, in the investigator's judgment, make continued participation in the study an unacceptable risk
- Note: If the subject's ALT and bilirubin levels decrease so that both are < 1.5 times ULN, the

investigator may decide to restart the medication and monitor on a weekly basis.

- Study medications will be discontinued in the event of any thrombosis

If subject’s platelet count goes above 200,000, the dose of study medication will be reduced.

As indicated on page 5, perhaps 2-3 of the 15 patients in the study might be at risk over a lifetime for a malignancy such as lymphoma, but it is not very likely to happen during the relatively short time course of the study. If 1 patient develops another type of malignancy or 2 patients develop a Non-Hodgkin Lymphoma during the course of the study, the study will be stopped. Prior to the study being restarted (if this is the desire of the investigators), there will be a formal request to re-open the study submitted to the FDA with a letter of support from Novartis.

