History of Thromboembolic Events

Thrombotic events can occur at any platelet count. Thrombotic/thromboembolic complications may result from excessive increases in platelet counts. Excessive doses of eltrombopag or medication errors that result in excessive doses of eltrombopag may increase platelet counts to a level that produces thrombotic/thromboembolic complications. In the controlled ITP clinical studies, one thrombotic/thromboembolic complication was reported within the groups that received eltrombopag and none within the placebo groups. Seven patients experienced thrombotic/thromboembolic complications in the ITP extension study.

Caution should be used when administering eltrombopag to patients with known risk factors for thromboembolism (e.g., Factor V Leiden, ATIII deficiency, antiphospholipid syndrome, etc.).

Malignancies and Progression of Malignancies

Stimulation of the TPO receptor on the surface of hematopoietic cells by eltrombopag may increase the risk for hematologic malignancies. In the controlled ITP clinical studies, patients were treated with eltrombopag for a maximum of 6 weeks and during this period no hematologic malignancies were reported. One hematologic malignancy (non-Hodgkin's lymphoma) was reported in the ITP extension study.

Cataracts

Cataracts were observed in toxicology studies of eltrombopag in rodents (see Non-clinical Information). The clinical relevance of this finding continues to be evaluated in all ongoing NOVARTIS sponsored clinical studies. To date, there is however, no evidence that eltrombopag increases the incidence nor progression of cataracts in patients who have received eltrombopag. In the controlled ITP clinical studies, cataracts developed or worsened in five (5%) patients who received 50 mg eltrombopag daily and two (3%) placebo-group patients. In the ITP extension study, cataracts developed or worsened in 4% of patients who underwent ocular examination prior to therapy with eltrombopag. A significant proportion of patients in the ITP clinical studies were also exposed to chronic corticosteroid administration.

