10. APPENDICES

1. SCHEDULE OF EVENTS ON THE LAST PAGE OF THE PROTOCOL (PAGE 25).

2. WEEKLY DOSE ADJUSTMENT FOR PLATELET COUNTS:

PLATELET COUNT	DOSE ADJUSTMENT
>200 Gi/L	dose reduced by at least 5%
50 to 200 Gi/L	Maintain current dose
<50 Gi/L and/or Significant Bleeding	Increase daily dose by at least 5% up to 75mg daily

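### The dose-adjustment table's increase row has no upper count limit, so bleeding above 200 Gi/L triggers an increase where the protocol elsewhere requires a reduction

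*Combined protocol and SAP*

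**What the plan says.** The table in Section 10, item 2, has three rows.

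- Above 200 Gi/L: "dose reduced by at least 5" per cent.
- From 50 to 200 Gi/L: "Maintain current dose".
- For "<50 Gi/L and/or Significant Bleeding": "Increase daily dose by at least 5% up to 75mg daily".

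Two other places address counts above 200 Gi/L. Section 3.1 says that "the dose of eltrombopag will be reduced whenever the platelet count exceeds 200Gi/L in order to prevent it from reaching 400Gi/L", and presents this as what the dosing guidelines explain. Section 4.4 says that if the "platelet count goes above 200,000, the dose of study medication will be reduced". Neither mentions bleeding.

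Section 6.3 gives the safety reason for a ceiling: "Thrombotic/thromboembolic complications may result from excessive increases in platelet counts". Section 4.4 adds that "Study medications will be discontinued in the event of any thrombosis".

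**The concern.** The first two rows sort patients by count alone. The third sorts them by count or by bleeding. Its linking words make bleeding sufficient at any count, its only limit is on dose, and the first two rows do not exclude bleeding patients. The rows therefore overlap, and the table does not say which prevails.

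Above 200 Gi/L the overlap matters most, because the two instructions point in opposite directions. Taken literally, the increase row raises the dose in the count range where the protocol wants it lowered to limit thrombotic risk.

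Bleeding at 50 Gi/L or more is a reasonable thing to plan for in this disease. Section 3.1 hypothesises more bleeding at a given count than in ITP, related to platelet dysfunction as well as to count. Section 8.3.1.1 expects function to improve without becoming normal. Section 3.1 also lets local doctors see patients after treatment starts at the main site, so someone outside the core team may be reading the table.

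**Working it through.** No sample size, power or error-rate figure bears on this point. The check is to apply the three rows to every combination of count band and bleeding, then compare the result with Sections 3.1 and 4.4.

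| Count (Gi/L) | Significant bleeding | Rows that apply | Sections 3.1 and 4.4 |
|---|---|---|---|
| Below 50 | No | Increase | Silent |
| Below 50 | Yes | Increase | Silent |
| 50 to 200 | No | Maintain | Silent |
| 50 to 200 | Yes | Maintain and increase | Silent |
| Above 200 | No | Reduce | Reduce |
| Above 200 | Yes | Reduce and increase | Reduce |

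Four of the six cells give one instruction and two give two.

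**Above 200 Gi/L with bleeding.** The increase row conflicts with the reduction row and with both sections of the text. Three statements say reduce and one says increase, so the increase row is the one to correct.

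**50 to 200 Gi/L with bleeding.** No other section chooses between maintaining and increasing. If maintaining prevailed here and reducing prevailed above 200 Gi/L, the bleeding trigger would do nothing at any count of 50 or more, and below 50 the count alone already triggers the increase. The trigger has a purpose only if it overrides maintaining in this band. That is the natural reading, but it is left unstated.

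**Distance between the instructions (illustrative only).**

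- Table minimum of 5% each way, before rounding: 1.05 / 0.95 = 1.11-fold above 200 Gi/L; 1.05 / 1.00 = 1.05-fold at 50 to 200 Gi/L.
- Suspension, 20 kg child (Appendix item 3.4, Table 1: start 40 mg, step 12 mg): 40 − 12 = 28 mg against 40 + 12 = 52 mg, so 52 / 28 = 1.86-fold above 200 Gi/L; 52 / 40 = 1.30-fold at 50 to 200 Gi/L.
- Tablets at 50 mg, assuming one 12.5 mg step: 37.5 mg against 62.5 mg, so 62.5 / 37.5 = 1.67-fold above 200 Gi/L; 62.5 / 50 = 1.25-fold at 50 to 200 Gi/L.

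The 12.5 mg step is an assumption: Section 3.1 lists that strength as available but sets no tablet step. The suspension example assumes that item 3.4 carries over the bleeding trigger, whereas its wording refers to platelet counts. It also uses the initial step, and item 3.4 allows intermediate doses.

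**Primary endpoint.** Section 8.3.1.1 counts any platelet count above 50,000/ul within the first 12 weeks as a response. Both overlapping cells lie at 50 Gi/L or more. Apart from a count of exactly 50, a treated patient who enters either cell in those 12 weeks has already responded, and a patient who enters later is outside the window. What could shift slightly is the proportion maintaining the increase and the bleeding comparisons, if investigators titrate differently.

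**The case against.** The strongest reply is that the case above 200 Gi/L is already answered. Section 3.1 states unconditionally that the dose comes down and presents this as the meaning of the dosing guidelines; Section 4.4 repeats it. On that view one loosely worded row creates no real doubt, and at 50 to 200 Gi/L the intended reading is plain.

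Most of this stands. A reader of the table alone might infer that the protocol leaves the action above 200 Gi/L open, or intends escalation in bleeding patients at any count. The full text does not support either inference. Nor is the overlap at 50 to 200 Gi/L a contradiction of equal weight; it is unstated precedence with an evident answer. What remains is that the table supplies the detailed adjustment rule, Section 3.1 points to it, and one row gives an instruction that the rest of the protocol forbids.

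It is also fair to say that nothing shows patients bleeding significantly above 200 Gi/L. Section 1.2 reports that 4 patients reached at least 100 Gi/L, in a series of 8 (5 from this study and 3 others), and that 6 of the 8 had fewer bleeding symptoms. It does not say how many passed 200 Gi/L or bled at high counts. A reader might take the dose ratios as a measure of harm. They compare two instructions and say nothing about the effect on counts or thrombosis.

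Finally, one could argue that weekly blood counts would catch any error quickly. Section 6.1 does describe weekly counts during dose adjustment, but Section 3.1 bases adjustment on monthly monitoring, and the Schedule of Events shows week 2, week 4 and then monthly draws. Weekly counts are not a firm safeguard.

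**Conclusion.** The point holds as a minor error in the dose-adjustment table. Above 200 Gi/L with significant bleeding, the increase row contradicts the reduction row and Sections 3.1 and 4.4. At 50 to 200 Gi/L with bleeding, the table omits a precedence that can be inferred.

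The size is small. Few patients are likely to be affected; that is a judgement, since the documents give no number. The 75 mg cap, the reduction text in Sections 3.1 and 4.4, and the rule stopping drug after any thrombosis all limit the harm, although the last acts only once a thrombosis has occurred. The primary endpoint is little changed and the sample size is untouched.

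A reader might also infer that the lack of a definition of significant bleeding is a fault in itself. The documents do not establish that: investigator judgement is workable in a 15-patient exploratory study, and the conflict above 200 Gi/L would exist under any definition.

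**What to change.** Replace the three rows with mutually exclusive ones.

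- Above 200 Gi/L: reduce, regardless of bleeding, in line with Sections 3.1 and 4.4.
- 50 to 200 Gi/L without significant bleeding: maintain.
- Below 50 Gi/L, or 50 to 200 Gi/L with significant bleeding: increase, up to 75 mg daily. The sponsor should confirm that the bleeding part of this row is what was meant.

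The minimum step sizes can stay as they are. The cost is one table in an amendment. Sections 3.1 and 4.4 need no change, and no extra tests, visits or patients are required.

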3. ELTROMBOPAG POWDER FOR ORAL SUSPENSION

Eltrombopag powder for oral suspension (Eltrombopag PfOS) is a reddish-brown to yellow powder contained inside an elongated sachet. Each sachet will contain eltrombopag olamine equivalent to 20 mg of eltrombopag per gram of powder.

3.1. Packaging and Labelling

Eltrombopag PfOS sachets will be packaged in a carton. Each carton pack will hold 35 sachets along with a plastic reconstitution container and a syringe-adapt cap. The pack will also contain an extra syringe-adapt cap as a spare. The contents of the label will be in accordance with all applicable regulatory requirements.

3.2. Preparation

The powder for oral suspension (PfOS) is presented as a reddish brown to yellow powder, which when reconstituted with water forms a reddish-brown suspension. The sachet should not be opened until ready for use. Add 9.5 mL of water drawn using a 10cc syringe into the provided plastic container. Cut open the sachet and add the entire content of the sachet into the container containing water. The container is capped and shaken for 10-20 seconds. The resulting suspension contains 2 mg/mL of eltrombopag dose. The prescribed volume (dose) is drawn through the syringe port on the cap with a syringe. Upon dosing, the rest of the remaining suspension in the container is discarded. The container and the syringe are rinsed with water and dried.

A fresh dose is prepared everyday just prior to the dosing and no storage of the reconstituted suspension is allowed.

3.3. Handling and Storage

Investigational product must be dispensed or administered according to procedures described herein. Only subjects enrolled in the study may receive investigational product, in accordance with all applicable regulatory requirements. Only authorized site staff may supply or administer investigational product. All investigational products must be stored in a secure area with access limited to the investigator and authorized site staff and under physical conditions that are consistent with investigational product-specific requirements. Eltrombopag PfOS will be stored according to the requirements listed on the label.

3.4. Dose Adjustment Guidelines for subjects receiving the suspension formulation

The dose of eltrombopag will be increased or decreased according to platelet counts as outlined above; these modifications will initially be in strength intervals of 30% (rounded up), but intermediate dosing levels may be used if the platelet response warrants it. The dose will be documented in the CRF.

Table 1: Dose Adjustment Guidelines – Suspension formulation

Weight (kg)	Initial dose (mg)	Initial dose (mL)	Adjust dose by (mg)	Adjust dose by (mL) ¹
8	16	8	5	2.5 ¹
9	18	9	6	3 ¹
10	20	10	6	3
11	22	11	7	3.5
12	24	12	8	4
13	26	13	8	4
14	28	14	9	4.5 ¹
15	30	15	9	4.5 ¹
16	32	16	10	5
17	34	17	11	5.5
18	36	18	11	5.5
19	38	19	12	6
20	40	20	12	6
21	42	21	13	6.5
22	44	22	14	7 ¹
23	46	23	14	7 ¹
24	48	24	15	7.5 ¹
25	50	25	15	7.5 ¹

1. For calculated doses of 18mg – 24 mg, patient should receive 20 mg dose (one sachet). For doses of 38 mg to 44 mg, the patient should receive 40 mg dose (two sachets). For doses of 58 mg to 65 mg the patient should receive 60 mg dose (three sachets).

References

Kühne T, Buchanan G, Zimmerman S, Michaels L, Kohan R, et al. A prospective comparative study of 2540 infants and children with newly diagnosed idiopathic thrombocytopenic purpura (ITP) from the intercontinental childhood ITP study group. *The Journal of Pediatrics*, 143, 5:605-608.



SCHEDULE OF EVENTS
“Pathobiology of Thrombocytopenia and Bleeding in Patients with Wiskott-Aldrich Syndrome.” Protocol #: 0801009600

	Screening	Day 1/Baseline	Week 2	Week 4	Months ⁴ 2 – 12	Months ⁵ 14 - 24	Months ⁶ 27 - 72
Evaluation and Management							
Informed Consent	x						
Bleeding Score ¹	x	x	x	x	x	x	x
Standard of Care							
Physical Examination	x	x	x	x	x	x	x
Urinalysis	x						
Admission Panel (Includes liver tests such as ALT, AST, bilirubin)	x	x	x	x	x	x	x
CBC with Platelet and Diff	x	x	x	x	x	x	x
Diagnostic Tests for Platelet Function							
PT/PTT	x						
D-Dimers	x						
Fibrinogen	x						
PFA ²					x		
Immature Platelet Fraction (Platelet Reticulocyte Count) ³	x	x	x	x	x	x	x
Single Platelet Flow Cytometry ⁷	x			x	x ⁸		

1. The Page bleeding score will be administered at each visit in order to semi-quantitatively assess bleeding
2. PFA (Platelet function Analysis) will be assessed once for WAS/XLT patients and control patients at month 2, provided platelet count is >50 k
3. IPF will be obtained with each Cornell in-clinic CBC where possible
4. Subjects will have their blood drawn monthly and be seen every 3 months during the first year
5. Subjects will have their blood drawn every 2 months and be seen every 4 months in the second year
6. Subjects will have their blood drawn every 3 months and be seen every 6 months in the 3rd – 6th years
7. Single Platelet Flow Cytometry tests will be performed by [name] at screening, once between months 1-3, and once after 1-2 years on study.

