Eltrombopag starting doses for children < 50kg will be scaled by body weight and the starting dose will be approximately 2 mg/kg once daily unless they are of East Asian origin in which case they will use approximately 1 mg/kg as their initial dose. This starting dose is based on the findings of GlaxoSmithKline's PETIT2 study: Eltrombopag for children with chronic immune thrombocytopenia (PETIT2): a randomised, multicentre, placebo-controlled trial.

This dosing schedule is based on those used in GlaxoSmithKline's 'PETIT' study: Eltrombopag in Pediatric patients with Thrombocytopenia from ITP.

For young children unable to swallow a tablet, eltrombopag powder for oral suspension (Eltrombopag PfOS) will be used. Each sachet contains eltrombopag equivalent to 20mg per gm of powder. Please see Appendix 3 for details and dose adjustment guidelines for subjects receiving the suspension formulation. Repeat assessment with the same testing will be performed at week 4. Dose adjustment will be based on the monthly monitoring of the platelet count.

The IPF will be measured at each visit with the CBC. Platelet count data will be collected throughout the study and used as part of the assessment of efficacy. Platelet count data will be collected as part of the CBC monthly during the first year of administration of study drug and at any dose change (eltrombopag or concomitant medication). If a subject continues on a stable dose during any stage of the study for greater than 4 weeks, a CBC (including platelet count) with differential will be performed no less frequently than every 4 weeks. Further information regarding reduction in use of concomitant medications for thrombocytopenia, use of rescue therapy, incidence and severity of bleeding and other symptoms associated with thrombocytopenia and infections will also be collected and summarized.

Platelet function will be assessed by whole blood flow cytometry as described by and in collaboration with [name] (see appendix for attached abstracts).

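### Footnote 1 of the suspension dosing table conflicts with the tabulated initial dose at six weights, and the size of a titration step depends on how the note is read

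*Combined protocol and SAP*

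**What the plan says.** For children under 50 kg, Section 3.1 says "the starting dose will be approximately 2 mg/kg once daily", with a lower start for one subgroup. Appendix 3.4 covers the suspension. On changes of dose it says "these modifications will initially be in strength intervals of 30% (rounded up", and it adds "but intermediate dosing levels may be used if the platelet response warrants it". Table 1 then lists, for each kilogram from 8 to 25, an initial dose in mg and mL and an amount to adjust by in mg and mL.

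Footnote 1 sets three bands. When the calculated dose lies between 18 and 24 mg, the "patient should receive 20 mg dose (one sachet". In the same way, 38–44 mg becomes 40 mg, given as two sachets, and 58–65 mg becomes 60 mg, given as three.

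The footnote mark stands on the column header "Adjust dose by (mL) ¹" and on the cells of that column at 8, 9, 14, 15, 22, 23, 24 and 25 kg. No mark stands on the initial-dose columns. Appendix 2 separately requires that an increase be no smaller than 5%.

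**The concern.** Six tabulated initial doses lie inside a footnote band and differ from the dose that the footnote assigns. A site working from this page could give either amount.

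The same gap runs into titration. Nothing says whether the bands apply to the initial dose as well as to adjusted doses, or whether the next step starts from the calculated dose or from the dose actually given. At 9 kg, one permissible reading turns the first increase into no change.

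The suspension is meant for young children who cannot swallow tablets. Under Section 8.3.1.1, response is a platelet count above 50,000/ul at any time in the first 12 weeks, and the dose may change only every 2 weeks, so a lost or shrunken step uses up titration time. Section 8.3.1.2 summarises extent of exposure. Appendix 3.4 has the dose entered in the CRF but does not say whether that means the calculated or the delivered dose.

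**Working it through.** **Inputs.** All come from Appendix 3.4 unless stated: weight w; initial dose 2w mg; step 30% rounded up; the bands 18–24, 38–44 and 58–65 mg, delivered as 20, 40 and 60 mg. The 5% minimum comes from Appendix 2.

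**Reproducing the table.** Step = ceil(0.30 × 2w). For example, 9 kg gives 5.4, so 6 mg; 12 kg gives 7.2, so 8 mg; 22 kg gives 13.2, so 14 mg; 25 kg gives 15 mg. The formula matches all 18 rows, so the table is consistent with its own rule. The difficulty starts with the footnote.

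**Initial dose, footnote against table.** Difference = (footnote − table) / table.

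| Weight (kg) | Table (mg) | Footnote (mg) | Difference |
|---|---|---|---|
| 9 | 18 | 20 | +11.1% |
| 11 | 22 | 20 | -9.1% |
| 12 | 24 | 20 | -16.7% |
| 19 | 38 | 40 | +5.3% |
| 21 | 42 | 40 | -4.8% |
| 22 | 44 | 40 | -9.1% |

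**First step up, three readings.**
- A: round the initial dose, and round the calculated dose after the step (initial + step).
- B: round the initial dose, add the step to the delivered dose, and round again.
- C: leave the initial dose as tabulated and round adjusted doses only.

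Each cell shows delivered dose before and after, the change, and the change as a percentage of the delivered dose.

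| Weight (tabulated step) | A | B | C |
|---|---|---|---|
| 9 kg (6 mg) | 20 to 20: 0 mg, 0% | 20 to 26: 6 mg, 30% | 18 to 20: 2 mg, 11% |
| 11 kg (7 mg) | 20 to 29: 9 mg, 45% | 20 to 27: 7 mg, 35% | 22 to 29: 7 mg, 32% |
| 12 kg (8 mg) | 20 to 32: 12 mg, 60% | 20 to 28: 8 mg, 40% | 24 to 32: 8 mg, 33% |
| 22 kg (14 mg) | 40 to 60: 20 mg, 50% | 40 to 54: 14 mg, 35% | 44 to 60: 16 mg, 36% |
| 25 kg (15 mg) | 50 to 60: 10 mg, 20% | 50 to 60: 10 mg, 20% | 50 to 60: 10 mg, 20% |

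Over all 18 rows, delivered step / tabulated step for the first increase runs from 0 to 1.50 under A, 0.67 to 1.11 under B, and 0.33 to 1.14 under C. The maximum is 12/8 = 1.50, at 12 kg under A. The 0% at 9 kg under A falls below the 5% minimum in Appendix 2.

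**First step down.** The ratio runs from 0.50 (12 kg: 20 to 16, 4 mg against 8) to 1.33 (9 kg: 20 to 12, 8 mg against 6) under A, and from 0.75 to 1.27 under B and C.

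**Later steps under A.** At 10 kg, calculated 38 and 44 mg are both delivered as 40 mg, so that step also vanishes. The largest ratio at any step up to 75 mg is 10/6 = 1.67, at 9 kg (calculated 24 to 30, delivered 20 to 30) and at 10 kg (calculated 44 to 50, delivered 40 to 50).

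**Row marks under C.** One step up or down reaches a band at 8, 9, 13, 14, 15, 16, 17, 22, 23, 24 and 25 kg. The rows at 13 kg (down to 18 mg), 16 kg (up to 42, down to 22) and 17 kg (down to 23) carry no mark. The other eight do.

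**The case against.** The footnote may be deliberate: a table of calculated doses followed by a whole-sachet rule, with the starting dose only approximate in any case. Alternatively, its mark sits only on the adjustment column, so it may not reach initial doses. Either choice would leave one initial dose per weight. The 30% is an opening interval, and intermediate levels are allowed. The mark on the column header could cover every row, and superscripts in text read from a PDF are weak evidence. Even under reading A, 14 of 18 rows have a first step up of 20% to 38%. The suspension concerns only some of 15 treated patients in a descriptive study.

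Most of this stands as a limit on size, but it does not settle the conflict. The two defences exclude each other, and the documents do not choose between them. If the note overrides the table, six printed initial doses are not the doses given. If it covers adjusted doses only, a calculated 24 mg is delivered as 24 mg at 12 kg but as 20 mg at 9 kg, and the 9 kg increase shrinks to a third. The allowance for intermediate levels concerns modifications; it does not say which initial dose applies.

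A reader might infer more than the documents support:
- *The note doubles steps.* In mg no step doubles under any of the three readings. The 60% at 12 kg is twice 30% only as a share of the rounded dose, and only under A.
- *The note cancels the step.* The loss of the first step occurs at one weight, 9 kg, and only under A.
- *The non-response rule is affected.* The patient stopping rule in Section 4.4.2 uses 1.5 mg/kg. Every initial dose in Table 1 exceeds this after rounding; the lowest is 20/12 = 1.67 mg/kg. Rounding does not change whether the threshold is passed.
- *Dose records will be wrong.* The plan has the dose documented. It does not say which dose, which is an ambiguity and not a shown error.

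**Conclusion.** The concern holds as a conflict between the table and its footnote, with consequences that depend on the reading. Read literally, the note contradicts the tabulated initial dose at six of 18 weights, by -17% to +11%. The first increase is 0 to 1.5 times the tabulated step, or 0% to 60% of the delivered dose against 30%. At 9 kg it is 0 mg if the initial and the stepped calculated dose are both rounded, 2 mg if only adjusted doses are rounded, and 6 mg if the step is added to the delivered dose.

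The six-weight conflict assumes that the note covers initial doses. The 0 and the 1.5 further assume that steps are counted from the calculated dose. The missing marks at 13, 16 and 17 kg matter mainly if the note covers adjusted doses only, and they rest on the marks as they appear in the extracted text. The effect on response is modest: under A the next calculated dose at 9 kg, 30 mg, lies outside the bands, so one adjustment interval is lost. How many children would take the suspension is not stated.

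**What to change.** Reconcile Table 1, footnote 1, the placement of its marks and the base from which each step is counted. Each weight should then show one delivered initial dose and one delivered step up and down, and each delivered increase should be checked against the minimum in Appendix 2. State in Appendix 3.4 that the CRF records the delivered dose. Which version stands is for the sponsor to decide; no view is taken here on which dose is right. The cost is the revision of one 18-row table and a few sentences. The sample size and the planned analyses do not change.
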